## Appendix D: International Working Group (IWG) Response Criteria in Myelodysplasia (Cheson, 2006)

Altering Disease Natural History	
Complete remission (CR)	Bone marrow: $\leq 5\%$ myeloblasts with normal maturation of all cell lines Persistent dysplasia will be noted a Peripheral blood: 
 
- Hemoglobin <math>\geq 11</math> g/dL
 
- Platelets <math>\geq 100 \times 10^9/L</math>
 
- Neutrophils <math>\geq 1.0 \times 10^9/L</math>
 
- Blasts 0%
 

Partial remission (PR)	All CR criteria if abnormal before treatment, except: Bone marrow blasts decreased by $\geq 50\%$ over pretreatment but still $> 5\%$ Cellularity and morphology not relevant
Marrow CR	Bone marrow: $\leq 5\%$ myeloblasts and decrease by $\geq 50\%$ over pretreatment Peripheral blood: if HI responses, they will be noted in addition to marrow CR
Stable disease (SD)	Failure to achieve at least PR, but no evidence of progression for $> 8$ weeks
Failure	Death during treatment Disease progression characterized by worsening of cytopenias, increase in % of bone marrow blasts, or progression to a more advanced MDS FAB subtype than pretreatment
Disease Progression (PD)	For patients with: 
 
• Less than 5% blasts: <math>\geq 50\%</math> increase in blasts to <math>> 5\%</math> blasts
 
• 5% - 10% blasts: <math>\geq 50\%</math> increase in blasts to <math>> 10\%</math> blasts
 
• 10% - 20% blasts: <math>\geq 50\%</math> increase in blasts to <math>> 20\%</math> blasts
 
• 20% - 30% blasts: <math>\geq 50\%</math> increase in blasts to <math>> 30\%</math> blasts
 
 Any of the following: 
 
• At least 50% decrement from maximum remission/response levels in granulocytes or platelets
 
• Reduction in Hgb concentration by <math>\geq 2</math> g/dL
 
• Transfusion dependence
 

a Dysplastic changes should consider the normal range of dysplastic changes (modification).

Source: Cheson BD, Greenberg PL, Bennett JM, Lowenberg B, Wijermans PW, Nimer SD, et al. Clinical application and proposal for modification of the International Working Group (IWG) response criteria in myelodysplasia. Blood. 2006; 108(2): 419-25.

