Duration of response will be calculated only for subjects who achieve CR, mCR, PR or HI for the MDS Cohort, CR or CRi for the AML Cohort. Duration of response is defined as the time from first response observed until relapse, PD or death. Duration of response will be censored at the last response assessment date that the subject is known to be progression-free for:

- Subjects who have not relapsed, progressed or died at the time of analysis.
- Subjects who have withdrawn consent or are lost to follow-up prior to documentation of progression.

Censoring rules are defined in [Table 4](#).

Duration of response will be analyzed using the KM method. Median duration of response along with two-sided 95% CI will be provided for each cohort and treatment group.

In addition, the duration of each specific subcategory of response in the MDS Cohort (CR, mCR, PR or HI) and in the AML Cohort (CR) will be summarized using standard descriptive statistics.

Relapse-free Survival (RFS)

Relapse-free survival is defined only for subjects who achieve CR or PR for MDS subjects, CR and CRi for AML subjects, and is measured as the interval from the date of first documented response to the date of disease relapse or death from any cause, whichever occurs first. Subjects who are still alive and relapse-free will be censored at the date of their last response assessment. The RFS curve will be estimated using KM method.

Median RFS along with two-sided 95% CI will be provided for each cohort and treatment group. The RFS at 6 and 12 months will be estimated and compared using Kaplan-Meier (KM) method.

Censoring rules are defined in [Table 4](#).

Cytogenetic Response

External central pathology/cytogenetic reviewers will review the morphologic/cytogenetic data from bone marrow aspirate (BMA), bone marrow biopsies (if performed) to determine whether a subject achieved a cytogenetic response (complete or partial cytogenetic responses for MDS subjects and cytogenetic complete response for AML subjects). For cytogenetic response evaluable subjects (ie subjects with baseline cytogenetic abnormalities), the number and percentage of subjects who achieve the cytogenetic responses will be summarized together with associated two-sided 95% CI.

MDS Cohort:

Progression-free Survival (PFS)

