Progression-free survival is calculated as the time from randomization to the first documented progression, relapse or death due to any cause during or after the treatment period, whichever occurs first. Subjects who are still alive and progression-free will be censored at the date of their last response assessment. The PFS curve will be estimated using KM method.

Median PFS along with two-sided 95% CI will be provided for each cohort and treatment group. The PFS at 6 and 12 months will be estimated and compared using Kaplan-Meier (KM) method.

A sensitivity analysis of PFS will be performed, censoring PFS at the time of subsequent systemic anticancer therapy if the subject did not progress before that time.

Transformation to AML and Time to AML Transformation

Number of subjects with transformation to AML and time to transformation to AML will be summarized. Time to transformation to AML is defined as the time from the date of randomization until the date the subject has documented transformation to AML (at least 30% of BM blats). Subjects who do not transform to AML will be censored at the date last disease assessment date. Median time to transformation to AML and associated two-sided 95% CI will be estimated using KM method.

AML Cohort:

HI

Rate of HI – erythroid response (HI-E), hematological improvement – platelet response (HI-P) and hematological improvement – neutrophil response (HI-N) according to IWG 2006 response criteria for MDS ([Appendix 17.2](#)), will be provided together with Wald asymptotic two-sided 95% CIs.

Table 4: Event and Censoring Rules for Progression-free Survival, Duration of Response, Time-to-Response and Relapse-free Survival

Situation	Date of Progression or Censoring	Situation Outcome
Censoring Rules for PFS and DoR		
Progression	If the first PD is a scheduled assessment then Date of first PD; If the first PD is an unscheduled assessment and no previous assessment, then Date of PD; If the first PD is an unscheduled assessment and has previous assessment, then Date of previous assessment (regardless of the response type).	Event
Death between scheduled assessments or within the first two missed scheduled assessments	Date of death	Event
No progression	Date of last adequate assessment with evidence of no PD	Censored
Death or progression after two or more missed scheduled assessments	Date of last adequate assessment with evidence of no PD; if no adequate assessment exists then censored at date of first dose	Censored

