17.2. International Working Group (IWG) Response Criteria in Myelodysplasia (Cheson, 2006)

Altering Disease Natural History	
Complete remission (CR)	
 ▪ BM Blasts \leq 5% 
AND
 
 ▪ All of the following peripheral blood values met: 
 ▪ Hemoglobin \geq 11 g/dL ▪ Platelets \geq 100 x10⁹/L ▪ ANC \geq 1.0 x10⁹/L ▪ Peripheral Blasts=0% 
Labs must meet criterion for at least 28 consecutive days. If not confirmed for 28 days then response should be mCR.
 
In addition
 
 ▪ The 7/3 rule should be applied to Hemoglobin. ▪ Platelets collected 3 days period following Platelet transfusion will not be used - ANC values that must be at least 14 days following a G-CSF application
Partial remission (PR)	
 ▪ BM Blasts decreased by \geq 50% over pretreatment but still $>$ 5% 
AND
 
 ▪ All of the following peripheral blood values met: 
 ▪ Hemoglobin \geq 11 g/dL ▪ Platelets \geq 100 x10⁹/L ▪ ANC \geq 1.0 x10⁹/L ▪ Peripheral Blasts=0% 
Labs Must meet criterion for at least 28 consecutive days.
 
In addition
 
 ▪ The 7/3 rule should be applied to Hemoglobin. ▪ Platelets collected 3 days period following Platelet transfusion will not be used 
ANC values that must be at least 14 days following a G-CSF application

Marrow CR	
 ▪ Bone marrow: $\leq 5\%$ myeloblasts and decrease by $\geq 50\%$ over pretreatment with baseline BM blast $>5\%$ 
AND
 
 ▪ Not all of the following peripheral blood values met or none are met: 
 ▪ Hemoglobin ≥ 11 g/dL ▪ Platelets $\geq 100 \times 10^9/L$ ▪ ANC $\geq 1.0 \times 10^9/L$ ▪ Peripheral Blasts=0% 
Peripheral blood: if HI responses, they will be noted in addition to marrow CR

Stable disease (SD)	Any evaluable time point where criteria for all other response categories (i.e., CR, PR, PD, Failure due to death, Not Assessable) are not met
Failure	Death during treatment

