Disease Progression (PD)	
 ▪ If condition for Transformation to AML and relapse after CR/PR are not verified ▪ For patients with: 
 ▪ Nadir value less than 5% blasts: $\geq 50\%$ increase in blasts to $> 5\%$ blasts ▪ Nadir value 5% - 10% blasts: $\geq 50\%$ increase in blasts to $> 10\%$ blasts ▪ Nadir value 10% - 20% blasts: $\geq 50\%$ increase in blasts to $> 20\%$ blasts 
AND ANY OF THE FOLLOWING
 
 ▪ $\geq 50\%$ decrement from max level of ANC and ANC < 1.0 GI/L 
OR
 
 ▪ $\geq 50\%$ decrement from max level of Platelets and Platelets < 100 GI/L 
OR
 
 ▪ Reduction from max level of Hgb ≥ 20 g/L and Hgb < 110 g/L 
OR
 
 • Transfusion dependence (apply to baseline TI subjects only)

^a Dysplastic changes should consider the normal range of dysplastic changes (modification).

Source: Cheson BD, Greenberg PL, Bennett JM, Lowenberg B, Wijermans PW, Nimer SD, et al. Clinical application and proposal for modification of the International Working Group (IWG) response criteria in myelodysplasia. Blood. 2006; 108(2): 419-25.

Altering Disease Natural History	
Disease transformation	Transformation to AML (30% or more blasts)
Relapse after CR or PR	
 • BM % blast \geq baseline % blast and BM % blast \geq 5% 
OR
 
 • \geq 50% decrement from max level of ANC and ANC < 1.0 GI/L 
OR
 
 • \geq 50% decrement from max level of Platelets and Platelets < 100 GI/L 
OR
 
 • Reduction from max level of Hgb \geq 20 g/L and Hgb < 110 g/L 
OR
 
 • RBC/platelet transfusion is given after CR/PR

Cytogenetic Response	
Complete	Disappearance of the chromosomal abnormality without appearance of new ones
Partial	At least 50% reduction of the chromosomal abnormality

Hematological Improvement (HI)	

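### The SAP's MDS progression rule needs a blast rise and a further fall in counts, so marrow-only progression below 30% blasts becomes stable disease and is lost or delayed in PFS and DoR

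*SAP*

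**What the plan says.** SAP 17.2, Disease Progression row (MDS), has three parts.

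- A precondition: "If condition for Transformation to AML and relapse after CR/PR are not verified". Transformation is its own category: "Transformation to AML (30% or more blasts").
- A blast limb: a rise of at least 50% from nadir, to above 5%, 10% or 20% depending on the nadir band.
- A count limb, introduced by "AND ANY OF THE FOLLOWING". Its items are a fall of at least 50% from maximum in ANC to below 1.0 or in platelets to below 100; a hemoglobin fall of at least 20 g/L from maximum to below 110 g/L; or "Transfusion dependence (apply to baseline TI subjects only").

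The stable disease row is the default: "Any evaluable time point where criteria for all other response categories" are not met.

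SAP 10.2 ends PFS at "first documented progression, relapse or death due to any cause during or after the treatment period". For the other endpoint, "Duration of response is defined as the time from first response observed until relapse, PD or death". Under SAP Table 4, a subject without PD is censored at the last adequate assessment that shows no PD.

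Protocol Appendix D prints the blast bands and then the list of count changes in its PD row, with no connecting word between them. Its Failure row reads "Disease progression characterized by worsening of cytopenias, increase in % of bone marrow blasts, or progression to a more advanced MDS FAB subtype" than pretreatment. SAP section 15 says only that the response derivations were updated for consistency with the IWG criteria.

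**The concern.** Three groups have no other marrow event below 30% blasts: subjects whose best response is mCR, subjects with HI only, and non-responders. The SAP's relapse row applies only after CR or PR. The protocol's row for progression or relapse after HI has no counterpart in SAP 17.2. For these subjects, a marrow that has clearly worsened is stable disease unless the counts also fall far enough.

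The SAP's definition of mCR requires at least one peripheral blood criterion to be unmet, so these responders will often start from low counts. A baseline transfusion-dependent subject cannot use the transfusion item at all.

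At stake are two MDS secondary endpoints. DoR is also the named example of a secondary endpoint that can keep the MDS cohort open at the futility analysis (Protocol 9.3.1, SAP 4.3.1).

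The event can be lost and not merely late. Protocol Table 3 schedules no marrow after the discontinuation visit, and the later telephone contacts collect survival, subsequent therapy and transformation (Protocol 6.15).

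**Working it through.** No stated figure in the plan bears on this point, so there is nothing to reproduce. The check applies the SAP 17.2 rows as logical rules.

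**Test subject (assumed values).** Transfusion dependent at baseline and not in CR or PR. ANC goes from a maximum of 0.6 to 0.5, platelets from 30 to 25, hemoglobin from 88 to 80 g/L.

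**Count limb.**
- ANC must reach 0.5 × 0.6 = 0.3; observed 0.5, not met.
- Platelets must reach 0.5 × 30 = 15; observed 25, not met.
- Hemoglobin must reach 88 − 20 = 68 g/L; observed 80, not met.
- The transfusion item is closed, because the subject was dependent at baseline.

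**Blast limb and SAP result.**

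| Blasts | Blast limb | SAP category |
|---|---|---|
| nadir 12% to 28% | 12 × 1.5 = 18; 28 is above 20: met | SD |
| nadir 8% to 19% | 8 × 1.5 = 12; 19 is above 10: met | SD |
| mCR, nadir 3% to 14% | 3 × 1.5 = 4.5; 14 is above 5: met | SD |

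**Boundaries of the gap.**
- With blasts 12% to 28%, the subject becomes PD if ANC falls to 0.3, or platelets to 15, or hemoglobin to 68 g/L.
- A baseline transfusion-independent subject who becomes dependent is PD.
- Blasts of 32% are transformation, not PD.
- A CR/PR responder with baseline 12% and nadir 4% whose blasts return to 12% is a relapse on marrow alone. A rise that stops short of baseline is not, but CR and PR require recovered counts, so the count and transfusion items of that row remain open. Hence largely, not fully, covered.

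**What happens to the endpoints.** If assessments continue, PFS and DoR run on to a later event; marrow is scheduled every third cycle, 3 × 28 = 84 days. If assessments stop, the subject is censored at the visit that showed the rise, because SD counts as no PD. Death after two or more missed scheduled assessments is also censored (SAP Table 4), and DoR is censored at new systemic therapy.

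**Texts side by side.**
- Appendix D, Failure row: a blast increase is one of several alternatives joined by or.
- Protocol 6.7.3: after at least 6 cycles, progression conveyed by central pathology is acted on without reference to counts.
- SAP 17.2, relapse after CR/PR: blasts alone can meet it.
- SAP 17.3, AML progressive disease: marrow blasts alone can meet it.
- SAP 17.2, MDS PD: blasts alone cannot meet it.

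**Plain OR instead of AND.** The three SD cases become PD. So does a subject with stable 12% blasts whose platelets fall from 30 to 15, whom the current rule classes as SD.

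**The case against.** The strongest reply is that the SAP has not contradicted the protocol's PD row. That row has no connector and the SAP has chosen one reading. This stands. A reader might infer that Appendix D's PD row says OR and that the SAP reversed it; the page does not show that. Whether AND departs from the published IWG 2006 criteria depends on the cited paper and cannot be settled here. What remains is the conflict with the Failure row, Protocol 6.7.3 and the SAP's other rules, plus the undeclared choice.

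The count limb also has a purpose. Protocol 7.2.2.1 says azacitidine causes cytopenias, particularly in the first 2 cycles, when hematology is taken on Days 1, 8, 15 and 22. The PD row measures falls from maximum and asks for no persistence. If counts alone were enough, drug effect could register as PD before the Cycle 3 marrow. Best response is taken before PD, so real responses could be cut off. This stands, and it rules out a plain swap to OR. It does not argue against letting blasts suffice.

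A reader might also infer that transfusions largely prevent a 2 g/dL hemoglobin fall, making the count limb almost unreachable. The documents do not support this. The 7/3-day rule appears in the CR, PR and HI-E rows, and the post-transfusion platelet exclusion in the CR and PR rows; the PD row states neither. Without them a post-transfusion peak could set the maximum and make the limb easier to meet.

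Finally, these are secondary endpoints in a Phase 2 study, and the rule is the same in both arms. Investigator-assessed ORR and best response are also reported (SAP 10.2), but the SAP does not provide investigator-assessed PFS or DoR as a check.

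**Conclusion.** The point holds in a bounded form. The SAP's MDS PD rule classes as SD a marrow rise that meets its own blast thresholds, stays below 30% and comes without a qualifying count fall. This affects mCR responders, HI-only responders and non-responders. PFS and DoR then run past the rise or are censored at it.

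This follows from the text and needs no assumption about frequency. Its size does: the documents do not say how many MDS subjects are cytopenic or transfusion dependent at baseline, nor how often progression is seen in marrow only. No event count can be derived. A reader might infer a bias toward one arm, but nothing in the documents establishes one.

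Two further readings go too far. Already cytopenic subjects are not shut out of PD, since a further large fall still qualifies. The primary ORR is at most marginally affected: the only route is a later response counted because an earlier PD was not recorded.

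**What to change.** In the SAP 17.2 PD row:

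1. Make the blast criterion sufficient on its own for PD in the main PFS and DoR analyses. Do not simply replace AND with OR.
2. Report definitions that use the count limb, including the current AND rule, as sensitivity analyses.
3. State whether the 7/3-day hemoglobin rule and the post-transfusion platelet exclusion apply to the counts used.
4. Declare the rule in SAP section 15 and reconcile it with the PD and Failure rows of Appendix D. If AND was intended, give the reason there.

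This concerns the derived analysis endpoint only, not when treatment is stopped.

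The cost is a small programming change and no new data. PFS and DoR become somewhat shorter. At a low nadir, a small rise would count: 4% to 6% qualifies (4 × 1.5 = 6, above 5%). The AND-rule sensitivity analysis will show how much depends on such cases.

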#### **6.7.6. Transfusion Assessment**

The following will be recorded for all transfusions the subject received within 56 days (8 weeks) prior to randomization, until 90 days after the last dose of subcutaneous azacitidine or durvalumab or the Treatment Discontinuation Visit, whichever occurs later:

- Type of transfusion (eg, RBC or platelet)
- Number of units
- Reason for transfusion
- Date of transfusion
- Hemoglobin value for which any RBC transfusion is given
- Platelet value for which any platelet transfusion is given.

Red blood cell transfusions administered for surgical procedures, significant hemorrhagic events, or other reasons documented as unrelated to MDS-associated anemia will not be counted in the assessment of baseline RBC transfusion requirements, efficacy, or progressive disease status.

Red blood cell transfusion-independent response or improvement will be assessed according to criteria from that of the IWG criteria for MDS (Cheson 2006) (Appendix D).

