**Appendix D: International Working Group (IWG) Response Criteria in Myelodysplasia (Cheson, 2006) (Continued)**

Altering Disease Natural History	
Disease transformation	Transformation to AML (30% or more blasts)
Relapse after CR or PR	At least one of the following: 
 
• Return to pretreatment bone marrow blast %
 
• Decrement of <math>\geq 50\%</math> from maximum remission/response levels in granulocytes or platelets
 
• Reduction in Hgb concentration by <math>\geq 1.5</math> g/dL or transfusion dependence
 

Cytogenetic Response	
Complete	Disappearance of the chromosomal abnormality without appearance of new ones
Partial	At least 50% reduction of the chromosomal abnormality
Hematological Improvement (HI)	
Erythroid response (HI-E) (Pretreatment $< 11$ g/dL)	Hgb increase by $\geq 1.5$ g/dL Relevant reduction of units of RBC transfusions by an absolute number of at least 4 RBC transfusions/8 weeks compared with the pretreatment transfusion number in the previous 8 weeks. Only RBC transfusions given for a Hgb of $\leq 9.0$ g/dL pretreatment will count in the RBC transfusion evaluation
Platelet response (HI-P) (Pretreatment $< 100 \times 10^9/L$ )	Absolute increase of $\geq 30 \times 10^9/L$ for patients starting with $> 20 \times 10^9/L$ Increase from $< 20 \times 10^9/L$ to $> 20 \times 10^9/L$ and by at least 100%
Neutrophil response (HI-N) (Pretreatment $< 1.0 \times 10^9/L$ )	At least 100% increase and an absolute increase of $> 0.5 \times 10^9/L$
Progression/relapse after HI	At least one of the following: 
 
• At least 50% decrement from maximum response levels in granulocytes or platelets
 
• Reduction in Hgb by <math>\geq 1.5</math> g/dL
 
• Transfusion dependence
 

AML = acute myeloid leukemia; Hgb = hemoglobin; RBC = red blood cell  
 Source: Cheson BD, Greenberg PL, Bennett JM, Löwenberg B, Wijermans PW, Nimer SD, et al. Clinical application and proposal for modification of the International Working Group (IWG) response criteria in myelodysplasia. Blood. 2006; 108(2): 419-25.

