15. CHANGES TO THE STATISTICAL ANALYSES SECTION OF THE PROTOCOL

Response derivations have been updated for consistency with IWG Response Criteria in Myelodysplasia (Cheson, 2006) and Modified IWG AML Response Criteria (Cheson, 2003).

IA requirements and definition of EE population have been detailed in order to specify that subjects assigned to Arm A, who received less than 3 cycles of durvalumab and continued under azacitidine monotherapy are to be excluded from interim analysis and/or in the EE population.

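### SAP 17.2 records any RBC or platelet transfusion after CR/PR as relapse in the MDS cohort, where the protocol requires transfusion dependence

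*SAP*

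**What the plan says.** SAP 17.2, in the row for relapse after CR or PR, lists five alternative triggers. The last is that "RBC/platelet transfusion is given after CR/PR". The hemoglobin trigger is a fall from the maximum of at least "20 g/L and Hgb < 110 g/L". The ANC, platelet and blast triggers each carry an absolute floor.

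Protocol Appendix D, citing the same 2006 publication, has no such floors. Its last relapse item is a hemoglobin fall of at least 1.5 "g/dL or transfusion dependence". Protocol 6.7.6 adds that RBC transfusions given for surgery, significant hemorrhage or other documented reasons unrelated to MDS anemia "will not be counted in the assessment of baseline RBC transfusion requirements, efficacy, or progressive disease status".

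The SAP's own progression row in 17.2 keeps the dependence concept: "Transfusion dependence (apply to baseline TI subjects only".

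On disclosure, SAP 15 says only: "Response derivations have been updated for consistency with IWG Response Criteria in Myelodysplasia".

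**The concern.** One transfusion is not transfusion dependence. On its plain reading, the SAP line turns a subject in confirmed CR or PR into a relapse on the date of a single RBC or platelet transfusion. Relapse is an event in three MDS secondary endpoints of the SAP: DoR, RFS and PFS. PFS is exposed because the SAP adds relapse to the event definition; protocol Table 2 and 9.6.1.2 count only progression or death.

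The trigger also depends on local decisions. The study is open-label, and protocol 8.1 leaves blood product support to institutional standards. Protocol Appendix O records the DMC's remark about potential late cytopenias with the combination. If transfusion practice or cytopenia differs between arms, part of the between-arm difference in these endpoints would reflect transfusion rather than loss of response.

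**Working it through.** The documents give no power, event count or expected median for DoR, RFS or PFS, so there is no planned figure to reproduce. The check is a comparison of texts, followed by a labelled illustration.

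**1. The relapse rows side by side.**

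| Item | Protocol Appendix D | SAP 17.2 |
|---|---|---|
| Marrow blasts | back to pretreatment % | at or above baseline %, and at least 5% |
| Granulocytes/ANC | fall of 50% or more from maximum | same, and ANC below 1.0 × 10⁹/L |
| Platelets | fall of 50% or more from maximum | same, and below 100 × 10⁹/L |
| Hemoglobin | fall of at least 1.5 g/dL | fall of at least 20 g/L (2.0 g/dL), and below 110 g/L (11 g/dL) |
| Transfusion | dependence | any RBC or platelet transfusion |

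In protocol Appendix D a 2 g/dL fall is a progression criterion, not a relapse criterion.

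**2. Hemoglobin: the SAP is stricter.** Taking both falls from the same maximum:

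| Maximum (g/dL) | Protocol: maximum − 1.5 | SAP: maximum − 2.0, and below 11 |
|---|---|---|
| 11.0 | ≤ 9.5 | ≤ 9.0 |
| 12.0 | ≤ 10.5 | ≤ 10.0 |
| 13.0 | ≤ 11.5 | < 11.0 |
| 14.0 | ≤ 12.5 | < 11.0 |

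This change delays relapse, while the transfusion change brings it forward.

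**3. Which transfusions add relapses.** SAP CR and PR require Hgb of at least 11 g/dL and platelets of at least 100 × 10⁹/L. For a responder whose maximum is 11.0, an RBC transfusion at Hgb 9.0 or below coincides with a hemoglobin relapse under both documents (11.0 − 9.0 = 2.0). One given above 9.5 meets neither hemoglobin rule (11.0 − 9.5 = 1.5). For a responder whose platelet maximum is 100, a transfusion at 50 or below coincides with the 50% fall in both documents; one given above 50 does not. The extra relapses come from transfusions above these levels, or where no qualifying count was recorded.

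**4. Route to the endpoints (SAP 10.2).**
- RFS: restricted to CR or PR in MDS, with relapse or death as the event. Every MDS subject in the analysis is exposed.
- DoR: covers CR, mCR, PR and HI. Only CR/PR responders are exposed through this row.
- PFS: progression, relapse or death. Again, only CR/PR responders are exposed.
- ORR: does not use the row.

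One dating question is open. SAP Table 4 moves a relapse found at an unscheduled assessment back to the previous assessment. The SAP does not say whether a transfusion date is such an assessment.

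**5. Illustration on assumed inputs.** Let true response duration be exponential with median M. Let first transfusions that meet no other relapse criterion occur at a constant monthly rate r, independently. Then:

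recorded median = ln 2 / (ln 2 / M + r); share of events that are transfusion only = r / (ln 2 / M + r).

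For M = 12, ln 2 / 12 = 0.0578:
- r = 0.01: 0.6931 / 0.0678 = 10.2 months; share 15%.
- r = 0.02: 0.6931 / 0.0778 = 8.9 months; share 26%.
- r = 0.05: 0.6931 / 0.1078 = 6.4 months; share 46%.

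For M = 6 the medians are 5.5, 5.1 and 4.2 months.

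Equal rates in both arms still dilute a difference. With a control median of 12 months and a true hazard ratio of 0.50, the recorded ratio is (0.5 × 0.0578 + r) / (0.0578 + r): 0.63 at r = 0.02 and 0.73 at r = 0.05.

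The documents supply neither r nor M, and the stricter hemoglobin rule is left out of this sketch.

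**The case against.** The strongest reply is overlap. Many transfusions in a CR/PR responder would follow a fall in counts that is already relapse under both documents, and the SAP's 7/3-day rule keeps a hemoglobin value taken within 3 days before a transfusion. That stands: r is not the overall transfusion rate, and the illustration cannot be read as an estimate. It does not remove the defect, because one platelet transfusion, or one RBC unit given above the count thresholds, is still a relapse.

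A reader might infer that every transfusion around surgery becomes a relapse. The documents do not settle this. The SAP neither repeats nor revokes protocol 6.7.6; if 6.7.6 governs, surgical and hemorrhagic RBC units drop out. It covers RBC only, so platelets remain.

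A reader might also infer that the protocol's 1.5 g/dL rule should simply be restored. That goes too far. Both tables cite a publication that is not among the documents, so which is faithful to it cannot be decided here. The SAP's requirement of Hgb below 11 g/dL also stops a drop from 14.0 to 12.5 being called relapse, which the protocol rule as written would do.

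The futility rule might seem to be at risk, because DoR is its named example of a secondary endpoint. The link is marginal: DoR is only an example within the third of three alternative conditions, and a cohort that meets none of them only might be terminated.

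Finally, disclosure is partial rather than absent, since SAP 15 does announce updated response derivations.

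**Conclusion.** Wrong as written. The transfusion trigger in SAP 17.2 conflicts with protocol Appendix D, does not carry over protocol 6.7.6, and differs from the dependence criterion in the SAP's own progression row. Following it would record some CR/PR responders as relapsed without dependence and on the wrong date. SAP 15 does not itemise this change or the hemoglobin, ANC, platelet and blast changes in the same row.

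The consequence is confined to secondary endpoints in the MDS cohort. It would be tempting to say that DoR, RFS and PFS are biased as a whole and in a known direction. The documents do not support that: mCR-only and HI-only responders are outside the row, and the transfusion and hemoglobin changes pull in opposite directions. Net size and direction cannot be derived. The fall from 12 months to between 10.2 and 6.4 months rests entirely on the assumed exponential model and assumed rates of 1% to 5% per month.

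**What to change.** In SAP 17.2, replace the transfusion trigger with transfusion dependence, defined operationally by units and time window, since Appendix D uses the term without defining it. State that the 6.7.6 exclusion of RBC transfusions unrelated to MDS anemia applies, and add a matching rule for platelets. Reconcile the hemoglobin, ANC, platelet and blast thresholds with Appendix D. List each retained departure in SAP 15 with its reason, and add a sensitivity analysis of RFS, DoR and PFS using the protocol's relapse definition. Say whether a transfusion date counts as an unscheduled assessment under Table 4.

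The cost is SAP wording and a change to one derivation. Protocol 6.7.6 already has type, units, reason, date and pre-transfusion value recorded, so no new data are needed.
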